5.6.3.2 Secondary Effectiveness Endpoint #2

The statistical analysis of secondary effectiveness endpoint #2 will consist of an estimate of the proportion of patients with LAA exclusion intra-procedurally (Visit 2) and at the Endocardial EP Ablation Procedure (Visit 5). The AtriClip effectiveness population will be the population for this analysis. Missing observations will be excluded.

The proportion will be calculated with subjects as the experimental unit. The numerator of the proportion will be the number of subjects with LAA exclusion at the Visit and the denominator will be the total number of subjects without a missing observation. LAA exclusion is defined as a lack of fluid communication (<3 mm residual communication with LAA and < 10mm residual pocket) between the LA and LAA. The endpoint will be presented separately for Visits 2 and 5 with the numerator and denominator, the proportion and its 95% two-sided exact binomial confidence interval.

5.6.3.3 Secondary Effectiveness Endpoint #3

The statistical analysis of secondary effectiveness endpoint #3 will consist of an estimate of the proportion of patients with acute procedural success of epicardial surgical procedure, defined as the percentage of subjects with successful electrical isolation/block of all pulmonary veins, as well as the "box". The ITT and PP populations will be used for this analysis. Missing observations will be excluded.

The proportion will be calculated with subjects as the experimental unit. The numerator of the proportion will be the number of subjects with acute procedural success and the denominator will be the total number of subjects without a missing observation. The endpoint will be presented for each analysis population with the numerator and denominator, the proportion and its 95% two-sided exact binomial confidence interval.

Statistical Analysis Plan		Page 16 of 22
Sponsor	Study	Version
AtriCure	DEEP Pivotal Study	Version 2.0

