7.2 Visit 2 – Epicardial Surgical Ablation Procedure

NOTE: At the time of scheduling the subject's Epicardial Surgical Ablation Procedure, sites are encouraged to schedule the subject's Endocardial EP Ablation Procedure, for 91-121 days following surgery. Scheduling the Endocardial EP Ablation Procedure at the time of the subject's surgical procedure will ensure the subject's EP procedure occurs within the protocol visit window.

The Epicardial Surgical Ablation Procedure (**See Section 5.1**) will be performed within 45 days of the subject consenting to the clinical study. If the Epicardial Surgical Procedure is delayed, the subject must be re-consented and baseline tests repeated if necessary, for protocol defined windows.

The following must be conducted and/or obtained prior to or during the Epicardial Surgical Ablation Procedure:

- Confirm Inclusion/Exclusion criteria
- Esophagoscopy
- Note: Esophagoscopy to be performed prior to the placement of access ports for the epicardial procedure.
- Transesophageal Echo (TEE) – (performed at the beginning of the surgical procedure prior to placement of access ports, to confirm study eligibility and rule out thrombus in the left atrium or LAA. If a thrombus is present in the left atrium or LAA on TEE, the subject should not have the surgical ablation procedure performed.)

- Surgical Procedure Details (including procedure times)
- Surgical Ablation Details (including ablation and lesion details)
- LAA Management Details
- TEE Assessment (following exclusion of LAA)
- Adverse Event Assessment
- Post procedure Heart Rhythm Assessment – 30 second ECG
- Medications Review: Anticoagulation/antiplatelet therapy administered during surgical intra-procedure

Note: If patient requires conversion to either a thoracotomy or sternotomy during the surgical ablation procedure, they should not receive the catheter ablation procedure, and will be followed for 12 months.

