2.1.3 Secondary Efficacy Endpoints

1. Exclusion of the LAA, defined as lack of fluid communication (<3 mm residual communication with LAA and < 10mm residual pocket) between the LA and LAA. This endpoint will be measured at the 12-month Visit (Visit 11). The AtriClip® effectiveness population will be utilized for this analysis endpoint.
2. Exclusion of the LAA, defined as lack of fluid communication (<3 mm residual communication with LAA and <10 mm residual pocket) between the LA and LAA. The endpoint will be measured at the intra-procedurally (Visit 2), at the Endocardial EP Ablation Procedure (Visit 5). The AtriClip effectiveness population will be utilized for this analysis endpoint.
3. Acute procedural success of epicardial surgical procedure, defined as the percentage of subjects with successful electrical isolation/block of all pulmonary veins, as well as the “box”.
4. Acute procedural success of endocardial catheter procedure, defined as the percentage of subjects with successful electrical isolation/block of all pulmonary veins and the “box”, as well as bi-directional block of the cavo-tricuspid isthmus.
5. Freedom from Atrial Fibrillation, Atrial Tachycardia, Atrial Flutter without AAD, defined as no documented event >30 seconds in duration (or for the entire length of an ECG tracking) with no utilization of AADs beyond the blanking and AAD optimization periods, except as previously failed without an increase in dose. This endpoint will be measured through the 12-month, 2, 3, 4, and 5-year visits (Visits 11-15) via continuous 24- hour ECG monitor.
6. Freedom from Atrial Fibrillation, Atrial Tachycardia, Atrial Flutter regardless of AAD, defined as no documented event >30 seconds in duration (or for the entire length of a 30 second ECG tracing) regardless of AAD usage. This endpoint will be measured through the 12-month, 2, 3, 4, and 5-year visits (Visits 11-15 via continuous 24-hour ECG monitor).
7. Freedom from any documented AF, atrial flutter, or atrial tachycardia lasting >10 minutes in duration through the 12-month follow-up visit in the absence of Class I or III AADs (with the exception of previously failed AADs at doses not exceeding those previously failed).
8. Change in Quality of Life, defined as the total AFEQT score measured at the 12-month follow-up visit minus the score at the baseline visit. The score will be calculated per the AFEQT scoring manual.

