5.2 Analysis Populations

Intent to treat patient population (ITT): The ITT subject population will include all subjects who have met all inclusion/exclusion criteria and on whom a procedure was attempted (defined as a subject who underwent induction of anesthesia).

Modified intent to treat patient population (mITT): The mITT subject population will include all subjects who attempted the Epicardial Procedure (defined as a subject who underwent induction of anesthesia) and have at least one post-procedure follow-up visit after the 2nd Blanking Period (with the 2nd blanking period defined as the 90-days post Endocardial Ablation Procedure) with non-missing primary effectiveness data.

Safety Population: The safety population will include all enrolled subjects that undergo induction of anesthesia.

Per protocol patient population (PP): The PP patient population will include all subjects who complete both the Epicardial Surgical Ablation Procedure and Endocardial EP Ablation Procedure.

AtriClip Effectiveness population: The AtriClip effectiveness population will include all ITT subjects for whom an attempt (entrance of the AtriClip into the chest wall) is made to place an AtriClip device.

The primary effectiveness analysis will utilize the mITT patient population as defined in this statistical analysis plan. The analysis will be repeated on the ITT and PP patient populations as supportive analyses. Secondary effectiveness analyses will be conducted on the mITT, the ITT and the PP patient populations. All safety analyses will utilize the safety population.

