All secondary endpoints for LAA exclusion will utilize the LOCF method for missing values. No missing values will be imputed for the remaining secondary endpoints. If a subject is missing a value for one of these secondary endpoints, they will not be included in the analysis of that endpoint. The number of patients with non-missing values will be reported for each endpoint.

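### Acute procedural success (secondary effectiveness endpoints #3 and #4) excludes missing observations without saying how an aborted, incomplete or untested procedure is scored, so the ITT rate can become a rate among testable subjects

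*SAP*

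**What the plan says.** - **Endpoint #3, epicardial stage.** SAP 2.1.3 says it is "defined as the percentage of subjects with successful electrical isolation/block of all pulmonary veins, as well as the" box on the posterior left atrial wall. SAP 5.6.3.3 sets the populations and the missing-data rule: "The ITT and PP populations will be used for this analysis. Missing observations will be excluded". It fixes the proportion by making the numerator "the number of subjects with acute procedural success and the denominator will be the total number of subjects without a missing observation".
- **Endpoint #4, catheter stage.** SAP 5.6.3.4 uses the same denominator and exclusion rule, adds bidirectional block of the cavo-tricuspid isthmus (CTI), and reports mITT, ITT and PP.
- **General rule.** SAP 5.3 states: "If a subject is missing a value for one of these secondary endpoints, they will not be included in the analysis of that endpoint". Protocol 9.9 says the same. Both promise the count of subjects with a value.
- **Population.** SAP 5.2: "The ITT subject population will include all subjects who have met all inclusion/exclusion criteria and on whom a procedure was attempted", an attempt being defined as induction of anesthesia. PP requires completion of both procedures.
- **Aborted procedures.** SAP 5.3 has a scoring rule for these only under safety, where an abort caused by a primary safety event is a safety failure. Acute success has no counterpart.

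**The concern.** An absent block result is unlikely to be unrelated to outcome. Where testing shows conduction, the protocol has the operator ablate again (Protocol 5.1.5 for the veins; Protocol 5.3.2 requires gap closure at the catheter stage). Many tested failures should therefore be converted to successes before the procedure ends. Procedures without success would tend to be those that could not be finished, which is the group that an exclude-if-missing rule can remove.

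If it does remove them, the row labelled ITT answers a different question: how often block is achieved among subjects whose procedure went far enough to be tested. Leaving the term undefined also allows the scoring of these subjects to be settled after results are known.

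**Working it through.** The documents give no expected rate, threshold, power or sample size for endpoints #3 and #4, so there is no figure of the plan's to reproduce. The check has two parts.

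**1. Can an ITT subject reach analysis without a block result?**

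- ITT membership is fixed at induction (SAP 5.2).
- Under Protocol 5.1.4, anesthesia is induced and the dual-lumen tube is then placed. If lung isolation is not achieved, the study procedure is not performed. An otherwise eligible subject stopped here is in ITT with no lesion and no test.
- Under Protocol 5.1.5, the right veins are tested during the right-sided work, the left veins after left clamping, and the box only once the roof and floor lines have been completed from the left. A procedure stopped in between may hold vein results but no box result. If one vein was shown not to be isolated, the composite has already failed; the SAP does not say whether such a subject is a non-success or missing.
- Being in atrial fibrillation does not by itself prevent testing, because entrance block alone is then accepted (Protocol 5.1.5 and 5.3.2).
- Subjects stopped for left atrial or appendage thrombus meet exclusion criterion 29, so they leave through the ITT definition and not through this rule.

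**2. How large is the effect?**

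Let N be the ITT subjects, k those untested and x the successes.

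- Rate if untested subjects are treated as missing: r = x/(N − k)
- Rate if they are counted as non-success: x/N = r × (1 − k/N)
- Gap: r × k/N

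With r = 95% (assumed):

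- 2.5% untested: 0.95 × 0.975 = 92.6%
- 5% untested: 0.95 × 0.95 = 90.3%
- 10% untested: 0.95 × 0.90 = 85.5%

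In whole subjects, taking N = 220 (the planned maximum, SAP section 4), with k and x assumed:

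| Untested k | Tested-only rate | Untested as non-success | Gap (points) |
|---|---|---|---|
| 0 | 209/220 = 95.0% | 209/220 = 95.0% | 0 |
| 5 | 204/215 = 94.9% | 204/220 = 92.7% | 2.2 |
| 11 | 199/209 = 95.2% | 199/220 = 90.5% | 4.8 |
| 22 | 188/198 = 94.9% | 188/220 = 85.5% | 9.5 |

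A lower tested rate changes little: at about 90% with k = 11, 188/209 = 90.0% becomes 188/220 = 85.5%, a gap of 4.5 points.

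The nearest figure in the documents is from the staged feasibility study (Protocol 1.0): 24 of the 25 subjects treated surgically received the endocardial procedure. That 4% (1/25) describes attrition before the catheter stage. It does not estimate how many epicardial procedures go untested.

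**The case against.** The strongest reply is that neither document equates untested with missing. Success means achieved isolation, and a subject whose lesion set was never completed could properly be recorded as a non-success under that definition. This stands. A reader might infer that the SAP removes every untested subject; the text only leaves that open.

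Three further inferences are tempting and should not be drawn.

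- **That conversion removes a subject from #3.** Protocol 7.2 says: "If patient requires conversion to either a thoracotomy or sternotomy during the surgical ablation procedure, they should not receive the catheter ablation procedure". That bars the later catheter stage. Nothing says that epicardial lesions or testing stop, and the objective in Protocol 2.0 covers an open procedure. Only a converted subject with no block result is at risk of exclusion from #3.
- **That the ITT and PP rows nearly coincide for #3.** PP requires both procedures. A subject with a tested epicardial result who then withdraws, is converted or refuses the second stage counts in ITT but not in PP. The point applies to #4 only: subjects who never have the catheter procedure have no endocardial result, so excluding them leaves ITT close to PP.
- **That study success is affected.** SAP 5.6 ties success to the two primary endpoints. Protocol 9.6.1 lists #3 and #4 as exploratory, and SAP 5.6.3 allows no inference on them.

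The plan is also fairly open. Numerator, denominator and non-missing counts are shown, SAP 5.4 reports population sizes with reasons for exclusion, and SAP section 7 promises listings. A careful reader could rebuild the all-ITT rate. What the summaries would not show is why an ITT subject lacks a block result, since the reasons in SAP 5.4 concern membership of a population.

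**Conclusion.** The concern holds as a gap in definition with a known direction of bias. If started but untested procedures are treated as missing, the ITT rate is too high by exactly the tested rate times the untested share. At a 95% tested rate that is about 2.4, 4.8 and 9.5 points for 2.5%, 5% and 10% untested. Both the 95% and the untested shares are assumptions, and with nobody untested the two rules agree. The consequence is limited to two descriptive endpoints. It still merits correction before analysis, because the rule is easy to state now and open to dispute once results are seen.

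**What to change.** - **SAP 5.6.3.3 (#3).** In the ITT analysis, count every subject without documented isolation of all pulmonary veins and the box as a non-success. Tie this to the SAP's ITT set: Protocol 9.5 defines ITT without the anesthesia requirement, and on that wording eligible subjects who never reached the operating room would also count.
- **SAP 5.6.3.4 (#4).** Use as denominator all subjects in whom the endocardial procedure was started. Count undocumented vein, box or CTI block as a non-success. State that subjects who never started the catheter procedure, including converted subjects, are outside this denominator.
- **Both.** Keep the tested-only proportion as a supportive row, and report the number untested with reasons.
- **Alignment.** Bring SAP 5.3 and Protocol 9.6.1 and 9.9 into line. The exclusion rule also sits in Protocol 9.9, and Protocol 9.6.1 specifies ITT and PP for #4.

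The cost is wording in both documents; the data are already collected. The reported rates for these exploratory endpoints may be somewhat lower, and #3 will count a few subjects in whom no ablation device was used. The supportive row covers the narrower technical question. The primary endpoints do not change.

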5.6.3.4 Secondary Effectiveness Endpoint #4

The statistical analysis of secondary effectiveness endpoint #4 will consist of an estimate of the proportion of patients with acute procedural success of endocardial catheter procedure, defined as the percentage of subjects with successful electrical isolation/block of all pulmonary veins and the “box”, as well as bi-directional block of the cavo-tricuspid isthmus. The mITT, ITT and PP populations will be used for this analysis. Missing observations will be excluded.

The proportion will be calculated with subjects as the experimental unit. The numerator of the proportion will be the number of subjects with acute procedural success and the denominator will be the total number of subjects without a missing observation. The endpoint will be presented for each analysis population with the numerator and denominator, the proportion and its 95% two-sided exact binomial confidence interval.

5.6.3.5 Secondary Effectiveness Endpoint #5

The statistical analysis of secondary effectiveness endpoint #5 will consist of an estimate of the proportion of patients with freedom from Atrial Fibrillation, Atrial Tachycardia, Atrial Flutter without AAD, defined as no documented event >30 seconds in duration (or for the entire length of an ECG tracking) with no utilization of AADs beyond the blanking and AAD optimization periods, except as previously failed without an increase in dose. This endpoint will be measured through the 12-month, 2, 3, 4, and 5-year visits (Visits 11-15) via cumulative 24- hour ECG monitor. The mITT, ITT and PP populations will be used for this analysis. Missing observations will be excluded.

The proportion will be calculated with subjects as the experimental unit. The numerator of the proportion will be the number of subjects with freedom from the aforementioned events and the denominator will be the total number of subjects without a missing observation. The endpoint will be presented through each visit for each analysis population with the numerator and denominator, the proportion and its 95% two-sided exact binomial confidence interval. A similar summary will be provided for each yearly visit; if a subject fails at a given year they will be counted as a failure for subsequent yearly visits.

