29. Patient has presence of thrombus in the left atrium or the left atrial appendage, determined by echocardiography (either at baseline TTE (or equivalent diagnostic test) or intraoperative TEE).
30. Patient has history of blood dyscrasia or clotting disorder (i.e., Idiopathic Thrombocytopenic Purpura [ITP] or Thrombotic Thrombocytopenic Purpura [TTP]).
31. Patient has contraindication to anticoagulation that in the opinion of the

CONFIDENTIAL

CONFIDENTIAL

	
investigator poses undue risk to the patient from participating in the endocardial EP procedure.
 
32. Patient has a documented thromboembolism within the previous six months prior to signing informed consent.
 
33. Patient has an atrial myxoma.
 
34. Patient has a mural thrombus or mural tumor.
 
35. Patient has a condition or congenital anomaly which prevents required surgical or catheter access.
 
36. Patient has co-morbid condition that, in the opinion of the investigator, poses undue risk of general anesthesia or port access cardiac surgery.
 
37. Patient is currently abusing drugs or alcohol.
 
38. Patient is currently or has participated in a clinical study in the last 3 months prior to signing informed consent. Participation in survey clinical studies with no treatment is not an exclusion criterion.
 
39. Patient has a psychological disorder that could interfere with provision of informed consent, completion of tests, therapy, or follow-up.
 
40. Patient has a condition that, in the opinion of the investigator, may jeopardize the patient's well-being and/or the soundness of this clinical study.
 
41. Patient has a pre-existing esophageal condition that required (or requires) endoscopic therapy or surgical treatment.

Duration of Treatment:	Treated subjects will be assessed for primary safety through 30 days post-epicardial ablation procedure and 7 days post-endocardial procedure. Primary effectiveness will be assessed through 12 months post endocardial ablation procedure. All treated subjects who complete both epicardial and endocardial procedures will be followed through 5 years.

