5.6.3 Secondary Effectiveness Endpoints

Analysis of secondary effectiveness endpoints will be based on descriptive statistics and nominal two-sided 95% confidence intervals for observed data, with methods as described in section 5.1.1. Secondary Effectiveness Endpoint #1 will be evaluated with a hypothesis test. The remaining secondary endpoints will be presented as exploratory analyses; no statistical inference will be performed.

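### Yearly rhythm endpoints #5 and #6 keep earlier failures in the denominator but drop event-free subjects with a missing visit, which biases years 2 to 5 downward even under random loss

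*SAP*

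**What the plan says.** SAP 5.6.3.5 (endpoint #5, freedom from AF, flutter or tachycardia without AADs) and SAP 5.6.3.6 (endpoint #6, the same regardless of AADs) use the same wording. Each endpoint is a proportion with an exact binomial 95% interval, given through 12 months and years 2, 3, 4 and 5 for the mITT, ITT and PP populations. On missing data, "Missing observations will be excluded" and "the denominator will be the total number of subjects without a missing observation". For the yearly summaries, "if a subject fails at a given year they will be counted as a failure for subsequent yearly visits".

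SAP 5.3 gives the general rule: "No missing values will be imputed for the remaining secondary endpoints", and "If a subject is missing a value for one of these secondary endpoints, they will not be included in the analysis of that endpoint". Protocol 9.9 says the same. LOCF and the worst-case, best-case and break-even analyses belong to the primary effectiveness endpoint (LOCF also to LAA exclusion). Neither document gives a censoring or time-to-event method for #5 or #6.

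SAP 5.6.3 limits these endpoints to descriptive statistics and "nominal two-sided 95% confidence intervals for observed data", and Protocol 9.6.1 lists them as exploratory. The follow-up they cover is long. The Protocol synopsis (Duration of Treatment) states: "All treated subjects who complete both epicardial and endocardial procedures will be followed through 5 years".

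**The concern.** The two rules treat failures and successes differently. Once a failure is recorded, the carry-forward sentence fixes that subject's status at every later year, attended or not. An event-free subject has a status at year k only if the year-k observation exists. As follow-up is lost, the denominator sheds event-free subjects and keeps all earlier failures, so the proportion falls for a reason unrelated to rhythm. The exact binomial interval is centred on that proportion and inherits the error.

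Endpoints #5 and #6 are the only rhythm-effectiveness endpoints measured at years 2 to 5, so the description of durability is at stake. Some permanent loss after 12 months is built in: under Protocol 4.4, subjects converted to sternotomy or thoracotomy exit after the 12-month visit. In the ITT analysis, those who had failed by then would stay as failures to year 5, and those who had not would disappear.

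**Working it through.** The documents state no expected value for #5 or #6, so there is no plan figure to reproduce.

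**Inputs**
- 12-month freedom 70%: the design value for the primary endpoint in Protocol 9.3, borrowed as an anchor.
- N = 182: Protocol 9.3, used for the worked counts and the coverage check.
- New failures after 12 months: not given. Assumed 5% a year, with 0% and 10% as alternatives.
- Loss after 12 months: not given (Protocol 9.3 allows about 20% attrition, but before the 12-month endpoint). Assumed 3%, 5% or 10% a year, permanent and unrelated to outcome.

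**Formula.** Take the 12-month visit as year 1. Let S_k be the true event-free share at year k, with S_0 = 1, and G_k the share still attending, with G_1 = 1. The rule as written reports

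P_k = S_k G_k / [ S_k G_k + Σ_{j≤k} (S_{j-1} − S_j) G_j ].

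Because G_j ≥ G_k for j ≤ k, the denominator is at least G_k, so P_k ≤ S_k. Equality needs no loss after an observed failure. The direction is therefore algebraic; only the size rests on assumed rates.

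**Worked case, 5% failure and 10% loss, year 5**
- S_5 = 0.70 × 0.95⁴ = 0.5702; G_5 = 0.90⁴ = 0.6561.
- Event-free and attending: 0.5702 × 0.6561 = 0.3741.
- Failures kept: 0.3000 + 0.0350×0.9 + 0.0333×0.81 + 0.0316×0.729 + 0.0300×0.6561 = 0.4011.
- Reported: 0.3741 / 0.7752 = 48.3%, against 57.0%; before rounding, −8.8 points.

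**Reported freedom, 5% new failures a year**

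| | Year 2 | Year 3 | Year 4 | Year 5 | Year-5 bias |
|---|---|---|---|---|---|
| True | 66.5% | 63.2% | 60.0% | 57.0% | |
| 3% loss | 65.9% | 61.9% | 58.2% | 54.5% | −2.5 |
| 5% loss | 65.5% | 61.1% | 56.9% | 52.8% | −4.2 |
| 10% loss | 64.4% | 58.8% | 53.4% | 48.3% | −8.8 |

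In counts, 182 subjects at 5% loss leave about 84.5 event-free and 75.5 failed at year 5: 84.5/160.0 = 52.8%. With no loss the bias is zero.

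**Other failure rates, 5% loss, year 5.** With no late failures, a constant 70% is reported as 65.5% (−4.5 points). With 10% new failures a year, the bias is −3.8 points.

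**Interval.** In simulation (N = 182, 5% failure), the nominal 95% exact interval at year 5 covers the true value about 91% of the time at 3% loss and 48% at 10% loss.

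**Intermittent misses.** Suppose visits are missed at random 10% of the time and subjects return, with 5% new failures a year. The year-5 bias is −2.4 points if a recurrence is still detectable later, and −1.4 if a recurrence in a missed year is never seen. With 10% new failures, never seen if missed, it shrinks to −0.5. It stayed downward in every scenario run.

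**After the fix.** A life-table estimate returns about 66.5%, 63.2%, 60.0% and 57.0% at 3%, 5% or 10% loss. Dropping earlier failures who miss the visit as well gives the same values, to simulation error, under permanent random loss.

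**The case against.** The strongest reply is that the asymmetry is a matter of reading. The carry-forward sentence may only be meant to stop a subject who failed at year 2 and is in sinus rhythm at year 3 from counting as a success. The SAP does not say outright whether that subject stays in the denominator when year 3 is missing, and SAP 5.3 removes subjects with a missing value. If such subjects are also excluded, the bias vanishes under permanent random loss. This stands as a caveat. But the sentence carries no attendance condition, and the endpoint is measured through each visit, so an observed failure already settles the later status. The unconditional reading is the more natural one, and either reading needs an edit.

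It can also be said that a downward error is conservative and that a shrinking denominator will be visible, since SAP 5.3, 5.4 and 5.6.3 require counts and accountability by visit. Visibility does not remove the bias. Nor is the error a dependable safety margin, because the net direction is open if loss depends on outcome.

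The rates are assumed, and permanent loss gives the larger figures. Protocol 7.19 keeps subjects enrolled when a phone visit fails, so some misses will be intermittent and the bias smaller. That stands.

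Three stronger inferences are not supported. A reader might take these values as the study's main long-term result, but Protocol 9.6.1 and SAP 5.6.3 make them exploratory without inference. A reader might infer a threat to trial success, but that rests on the two primary endpoints (Protocol 9.7, SAP 5.6). A reader might say that dropout alone sets the error, but at 5% loss it runs from −4.5 to −3.8 points as the yearly failure rate goes from 0% to 10%.

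**Conclusion.** The point holds for the rule as written. With earlier failures carried forward regardless of attendance and event-free subjects excluded when missing, the yearly proportions for #5 and #6 and their exact intervals are biased downward at years 2 to 5, even under loss unrelated to outcome. The size depends on loss, failure rate and event-free share, none of which the documents give after 12 months. Under the stated assumptions the year-5 error is −2.5 to −8.8 points for 3% to 10% permanent yearly loss, and about −1.4 to −2.4 points for 10% intermittent misses with 5% new failures a year. The consequence is confined to the reported long-term rhythm durability. It should be corrected before the yearly analyses, but no success criterion depends on it.

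**What to change.** In SAP 5.6.3.5 and 5.6.3.6, estimate cumulative freedom through each annual visit with a life-table (or Kaplan-Meier) estimator. Use the annual visits as the intervals, because monitoring after 12 months is a 24-hour recording at those visits (Protocol 7.15). Censor event-free subjects at their last evaluable monitor, give 95% intervals from Greenwood's variance on the log-log scale, and state the non-informative censoring assumption. In the simulation above, those intervals covered the true value about 95% of the time at every loss rate tried.

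If simple proportions are kept, apply one attendance rule to both groups: earlier failures and event-free subjects both leave the year-k denominator when the year-k visit is missing. This removes the bias under permanent random loss. Neither option recovers a recurrence that falls in a missed year and is never recorded.

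The cost is a short SAP amendment, for which SAP section 6 already provides, and one standard procedure. No new data are needed.
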